The Remote Dielectric Sensing (ReDS) System is a non-invasive device that includes two sensors and a bedside console, and it is designed for the measurement of lung fluid using extremely low power electromagnetic waves. Fluid readings are displayed in volume percentage units. The ReDS Pro System V2.7 system has CE approval (3900874CE01) and FDA clearance. The Bedside Console consists of an embedded computer with a touch-screen display. The device is managed by computer software, which analyzes the measured signals and displays the measurement results. The console includes an electronic module and a wireless communications module. The system is portable, available at the patient's bedside and is AC-powered from a standard wall electrical outlet. The Sensor Unit is applied and positioned on the patient thorax according to anatomical markers over the patient clothes. The ReDS readings are stored locally on the device without any patient identifiers.

The ReDS ICU configuration is intended to allow continuous monitoring in the ICU setting, and except from the following main modifications the configuration is identical to the CE-marked ReDS Pro System V2.7 device: the sensors are converted to low-profile adhesive patch-sensors that are attached using standard biocompatible tape to the patient's skin for 48 hours in ICU setting. The sensors are disposable and intended for single-patient use. Cables can be detached and reattached by connectivity ports along the cable to support sensors replacement. A small tiltmeter to track chest sensor's orientation was added to support recording of postures. Additionally, the system software has been updated to support continuous monitoring.

The ReDS ICU configuration is intended for an observational study in the ICU setting. No immediate or long-term risks are anticipated. In both configurations, the ReDS system is non-invasive and uses radiofrequency waves at a power level, which is more than 200 times below the level that requires testing (i.e. exemption level) according to SAR safety (FCC and European regulations) and below 60601-1-2 emission limits. The system uses a low-voltage DC medical power supply and conforms to medical electrical safety standards. The adaptations to the sensors preserve the safety features of the tested version and can therefore be considered safe. The sensors were tested for safety, and the results met the required criteria. The software changes support continuous measurement and are not expected to introduce any safety risk. The patches are attached to the patient skin by a 3M medical transfer tape approved for its biocompatibility when adhered to the skin. We will monitor patient skin periodically for any irritation that may be caused by the tape or by the back sensor due to continuous use. The ReDS System will be used under supervision of a trained operator.

Based on the above, we summarize that except for above detailed modifications the ReDS ICU system is identical to the CE-marked ReDS V2.7 certified version and is safe to use in this observational clinical study.

3. INFORMATION ON THE MANUFACTURER

Sensible Medical Innovations LTD.
[name]
T. [name]
Email: [contact]

<https://sensible-medical.com/>

Manufacturer Statement of Compliance for Investigational Device

Manufacturer: Sensible Medical Innovations LTD.

Medical device under investigation: ReDS Pro System V2.7

Clinical investigation plan title: Evaluation of ReDS v2.7 and ReDS ICU in patients with heart failure

Clinical investigation reference no. / ID no.:

The manufacturer of the above investigational device hereby confirms that the investigational device in question conforms to the applicable essential requirements set out in Directive 93/42/EEC on medical devices, apart from the aspects covered by the clinical investigation and that, with regard to those aspects, every precaution has been taken to protect the health and safety of the subjects. This includes, where appropriate, technical and biological safety testing and pre-clinical evaluation, as well as provisions in the field of occupational safety and accident prevention, taking into consideration the state of the art;

Manufacturer: Sensible Medical Innovations LTD.

Medical device under investigation: ReDS ICU System

Clinical investigation plan title: Evaluation of ReDS v2.7 and ReDS ICU in patients with heart failure

Clinical investigation reference no. / ID no.:

The manufacturer of the above investigational device hereby confirms that the investigational device in question is based on the CE marked device (ReDS Pro System V2.7), using the same bedside console configuration which includes main electronics, power components and software. The main modification includes replacing the applied non-contact sensors used for spot measurements, with slim skin-patches sensors design which are single-patient-use and utilized for monitoring patients inside the ICU under the supervision of a trained professional during an observational study. An assessment of the safety implications of the modifications has been performed. Instructions for use and testing were adapted accordingly. Hence, device modifications related to the clinical study in the ICU do not raise any issue of electrical safety or biocompatibility. Other risks specific for the use in ICU will be monitored, assessed, and reported in accordance with GCP requirements. The manufacturer declares that the noted device is safe for use as an investigational device in an observational clinical study in Rigshospitalet Hospital, Copenhagen, Denmark. For detailed comparison to the CE marked device see investigator brochure.

4. PURPOSE

Over the last 30 years, the prognosis for patients with systolic heart failure (HF) has improved significantly, including prolonged life-expectancy, due to pharmacological treatments and cardiac devices (1). Despite these improvements in treatment, HF remains a major cause of morbidity and mortality, with almost 1 million patients admitted for HF annually in the United States (2), and the 5-years mortality rate remains near 50% (3). Although, the rates of HF hospitalization have decreased by nearly 30% during the past decade (4), there has not been any reduction in readmission after HF hospitalization. Thus, the latest studies show that HF readmission rates range between 19%-31% at 30 days (5) and around 50% at 6 months (6).

Re-hospitalization in patients with HF is often due to excess lung fluid and congestion (7). Prevention of HF hospitalization is important as it may lead to excess mortality and is an additional economic burden for the community (8). Early identification of subclinical congestion may prevent some HF exacerbation (9). Studies have reported that early detection of lung impending volume overload by pulmonary artery pressure guided therapy (e.g. CardioMEMS) in patients with HF is effective on patient behavior (e.g. medicine compliance) and adjusting pharmacological therapy to avoid re-hospitalization (10,11).

Continuously hemodynamic monitoring is essential in critically ill patients in an intensive care unit (ICU) who requires vasopressor, vasodilator and inotropic therapy (12). Right heart catheterization (e.g. Swan-Ganz) is the gold standard of hemodynamic monitoring but it is invasive and costly.

ReDS is a non-invasive device designed for quantifying lung fluid using low power electromagnetic waves. Studies has described the potential of ReDS to be used to track fluid status and guide medical management in HF patients (13,14). Furthermore, it has been reported that ReDS measurements of lung fluid is significantly associated with findings on chest computed tomography (CT) (14,15) and highly correlated to measures obtained through right heart catheterization (16). However, description of the feasibility and evaluation of ReDS ICU measurements of lung fluid in HF patients in ICU settings have not been studied before. There is a need for studies exploring non-invasive approaches of continuous hemodynamic monitoring to have alternatives to the invasive methods currently available.

We hypothesize that ReDS 2.7 allows for the identification of pulmonary congestion in out-patients before they develop symptomatic HF exacerbation and that the measurements are correlated with the CardioMEMS measurements. The aim of the out-patient part of the trial is to evaluate ReDS V2.7 efficacy in measuring lung fluid compared to pulmonary artery pressure guided therapy (CardioMEMS) in HF patients in the outpatient clinic under article 82 of the medical device regulation. The CardioMEMS HF System is CE marked and currently used in clinical practice at specialized hospitals in Denmark in patients with HF and NYHA functional class III.

We hypothesize that ReDS ICU allows for hemodynamic monitoring of ICU-patients continuously and that ReDS ICU provides hemodynamic measurements that are highly correlated with the Swan-Ganz measurements. We expect that changes to upper body-position will not affect the fluid parameter measured by ReDS ICU while the raised leg test, which increases the preload, will increase the fluid parameter measured by ReDS ICU. The aim of the ICU-patient part of the trial is to evaluate the feasibility of ReDS ICU system in critical-ill patients in an ICU setting under article 82 of the medical device regulation.

ReDS Pro System V2.7 and ReDS ICU are the same system, as described in the investigators brochure with only minor modifications (Appendix 02.02b). For the ReDS Pro System V.2.7, we will conduct an investigator-initiated study of already CE approved medical advice and for the ReDS ICU System we will test this prototype without the intention of obtaining CE-approval.

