5. METHODS

The study is an investigator-initiated, prospective cohort, single site study. The study has two parts: one for ICU patients and one for out-patient clinic patients. The study will take approximately 21 months to complete. Inclusion is expected to run from May the 1st, 2022 or as soon as possible thereafter and will continue until 10 patients have been included in out-patient part and 15 patients in the ICU part. The inclusion period is expected to be 21 months.

In the ICU study, the patient will have a Swan-Ganz catheter and an arterial catheter inserted as part of standard clinical practice and transthoracic echocardiography is likewise routinely performed. If the patient is eligible and after giving informed consent, the ReDS ICU system is applied for 48 hours continuously monitoring, whereafter it will be removed, and the patient's participation in the study is completed. During the inclusion in the study, the following data will be recorded:

- 1) Body position (Upper body elevation, left or right recumbent position)
- 2) ReDS ICU Lung Fluid parameter

- 3) ReDS ICU tilt parameter
- 4) Changes in patient body position

Before initiating the following interventions, the patient is required to have been hemodynamic stable for at least 1 hour, with a mean arterial pressure (MAP) around 65 mmHg and a maximum fluctuation of vasopressor-need of 25%. During the 48 monitoring, the following tests will be done:

- 1) Raised leg test – Both legs raised to 45° for 10 minutes.
- 2) Upper body elevation test - Starting from 30° the upper body is elevated to 45° then back to 30°, then 15° and back to 30°.
- 3) Left and right lateral recumbent position to 15° test – First left lateral recumbent position for 10 minutes then back to supine, then right lateral recumbent position for 10 minutes and then back to supine.
- 4) PEEP test – 5 cmH₂O increase PEEP for 10 minutes.

For all interventions, changes in HR, MAP, dPAP, mPAP, CO, SAT and ReDS ICU parameters (tilt and lung fluid) will be recorded 10 minutes prior, during and 10 minutes following completion of each test (1-4) . The completion of all interventions is estimated to take about 3 hours. The intervention will be paused if necessary.

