In the out-patient part, if the patient is eligible and provides informed consent, the patient will have 4 measurements of lung fluid, which will be done as home-visits by a study designated healthcare worker. The first visit will be after inclusion and the following visits will be 14 (+/-5) days, 28 (+/-5) days and 42 (+/-5) days after the first visit.

The visits are expected to take no more than 1 hour each. During each visit the following data will be recorded:

- 1) Height (only recorded at first visit) and weight (recorded each visit)
- 2) NYHA functional class
- 3) Presence of peripheral oedema
- 4) Orthopnea
- 5) Rales by auscultation
- 6) CardioMEMS measures
- 7) ReDS v2.7 measures lung fluid parameter

Endpoints

Primary endpoints

ICU part:

- Correlation between ReDS ICU fluid parameters and Swan-Ganz measurements including right atrial pressure, pulmonary wedge pressure, mPAP and dPAP.

Out-patient part:

- Correlation between ReDS v2.7 fluid parameters and CardioMEMS measurements

Secondary endpoints

ICU part

- Changes in ReDS ICU fluid parameters following changes in Positive End Expiratory Pressure.
- Changes in ReDS ICU fluid parameters following raised leg test.
- Changes in ReDS ICU fluid parameters following changes in body position.
- Changes in ReDS ICU fluid parameters following changes administration of diuretics and inotropic/inodilators

Out-patient part

- Correlation between ReDS v2.7 fluid parameters and body weight
- Correlation between ReDS v2.7 fluid parameters and CardioMEMs measure
- Correlation between ReDS v2.7 fluid parameters and dyspnea symptom evaluated by NYHA class.

SAFETY

Safety assessments will consist of registration and recording of adverse events (AEs), adverse device effects (ADEs), Serious Adverse Events (SAEs) and Serious Adverse Device Effects (SADEs). AEs, ADEs, SAEs and SADEs will be recorded during ReDS Pro System v2.7 and ReDS ICU monitoring time.

The following adverse device events (ADE) can be expected from both devices: Localized rash and redness of the skin.

Regarding, SAEs: The population of interest is vulnerable, and hospitalizations, prolonged ICU stay (ICU part), changes to medical therapy and death are considered likely.

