Specifically trained medical personnel will be present during the study visits and secure adequate assessment of the relevant safety parameters listed above, along with timely and accurate treatment of possible complications to study procedures. If it is medically necessary in the opinion of the investigator or if it is the wish of patients, the patient will be withdrawn from the study. At any time can the patient withdraw from the study. Patients who withdraw from the study will not be replaced by others.

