6. STATISTICAL CONSIDERATIONS

At the Heart Center ICU, Rigshospitalet, 20-40 patients with HF is admitted monthly from this patient population, 5-10 will require Swan Ganz monitoring and will eligible for the present study.

Around 30 patients have a CardioMEMS sensor implanted and are followed at the out-patient HF clinic at Rigshospitalet.

For this pilot study, we estimate that 15 patients in the ICU part and 10 patients in the out-patient part will be sufficient to evaluate the feasibility of the ReDs systems.

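### The no-effect expectation for upper-body position has no size attached and rests on 15 patients, and the fixed step order mixes each position with time and carry-over

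*Protocol*

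**What the plan says.** Section 4 (Purpose) sets out two expectations for the ICU part. One is that "changes to upper body-position will not affect the fluid parameter measured by ReDS ICU"; the other is that raising the legs will increase that parameter. The same section gives the purpose of this part: "The aim of the ICU-patient part of the trial is to evaluate the feasibility of ReDS ICU system".

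Section 5 (Methods) lists as a secondary ICU endpoint "Changes in ReDS ICU fluid parameters following changes in body position". The leg-raise endpoint has the same form.

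Section 5 also fixes the manoeuvres. For elevation (test 2): "Starting from 30° the upper body is elevated to 45° then back to 30°, then 15° and back to 30" degrees. For lateral position (test 3): "First left lateral recumbent position for 10 minutes then back to supine", followed by the right side and a return to supine. Haemodynamics, tilt and lung fluid are recorded "10 minutes prior, during and 10 minutes following completion of each test (1-4"). The four tests together are expected to take about 3 hours.

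On numbers, Section 6 says that "15 patients in the ICU part and 10 patients in the out-patient part will be sufficient to evaluate the feasibility of the ReDs systems". Section 5, under Safety, adds: "Patients who withdraw from the study will not be replaced by others".

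**The concern.** The two expectations are of different kinds but share one form of endpoint. A plain change can support the claim that leg raising increases the reading. It cannot support the claim that posture leaves the reading unaffected unless someone has said how small a shift counts as none. Without that, small numbers and noisy readings both work in favour of the stated expectation.

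The step order is a separate matter. In every patient the 15° step follows the 45° step, and the right side follows the left. Any drift in lung fluid, sensor contact or haemodynamics, and any residue of the previous step, is then part of the later position's apparent effect. It can create a posture effect or hide one.

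What is at stake is how the device can be read. It is meant for 48 hours of continuous monitoring, and Section 5 records tilt and position changes alongside lung fluid, so sensitivity to posture bears on whether a moving reading means moving fluid.

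**Working it through.** **Inputs.** From the protocol: n = 15 in the ICU part; each patient is their own control; withdrawals are not replaced. The protocol gives no alpha, test, effect size, SD or margin, so there is no figure of its own to reproduce. Assumed here: a paired t analysis at the 5% level, with shifts expressed as d = mean change divided by the SD of the within-patient change.

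**Precision.** Half-width = t(n−1)/√n, in SDs of the change.
- 90%: 1.761/√15 = 1.761/3.873 = 0.45 SD
- 95%: 2.145/3.873 = 0.55 SD

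**Chance of missing a real shift.** Power comes from the noncentral t with 14 degrees of freedom and noncentrality d√15. For d = 0.5 this is 0.5 × 3.873 = 1.94.

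| True shift (d) | Power, two-sided 5% | Power, one-sided 5% |
|---|---|---|
| 0.3 | 19% | 30% |
| 0.5 | 44% | 58% |
| 0.6 | 58% | 71% |
| 0.8 | 82% | 90% |

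At d = 0.5 the shift is missed 56% of the time (two-sided) or 42% (one-sided). Two-sided power reaches 50% at d = 0.54 and 80% at d = 0.78. With 12 evaluable patients, two-sided power at d = 0.5 falls to 35%. If 0.5 SD means the between-patient SD of the level instead, then d = 0.5/√(2(1−ρ)). Two-sided power is then 44% at a within-patient correlation of 0.5, 64% at 0.7 and 81% at 0.8.

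**If no effect were tested as equivalence.** The rule is that the 90% interval lies inside ± the margin. With a true shift of zero and n = 15, simulated power is 20% for a margin of 0.5 SD, 43% for 0.6, 74% for 0.75, 81% for 0.8 and 96% for 1.0. The reason is visible by hand: with a 0.5 SD margin and a half-width of about 0.45 SD, the mean must fall within about 0.5 − 0.45 = 0.05 SD of zero, while its standard error is 1/√15 = 0.26 SD. About 36 patients would give 80% power at that margin.

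**Step order.** Number the five stages of test 2 as 0 to 4 (30°, 45°, 30°, 15°, 30°). For illustration, assume equal stage lengths and a steady drift of b per stage.
- Baseline before the test only: 45° carries a drift error of 1b and 15° carries 3b, a difference of 2b.
- Mean of before and after the whole test (centred on stage 2): 1b − 2b = −b for 45° and 3b − 2b = +b for 15°. The difference is still 2b.
- Mean of the rests on either side of each step: (0 + 2)/2 = 1 for 45° and (2 + 4)/2 = 3 for 15°. The drift error is zero for both.
- Order alternated 8 to 7 with the pre-test baseline only: (8×1 + 7×3)/15 = 1.93b and (8×3 + 7×1)/15 = 2.07b. The difference shrinks to 0.13b, but about 2b remains in each.

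The two measures therefore do different jobs. Bracketing rests remove steady drift. Alternation stops residue from the previous step always falling on the same position, which bracketing cannot do because the middle rest may itself be contaminated. Test 3 has the same structure.

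**The case against.** A reader might infer that a non-significant change is the planned route to confirming no effect. The protocol does not say so. It names no test, alpha or decision rule, and a mean change with an interval would satisfy the endpoint as written. The choice may properly sit in a statistical analysis plan that is not shown. The posture statement is also worded as an expectation, the endpoint is secondary, and the ICU part is a feasibility pilot. All of that stands.

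It is also tempting to say that a half-SD shift would be missed more often than not. That holds only under a two-sided 5% test on the SD of the change. It reverses with a one-sided test, with a shift above 0.54 SD, or with a between-patient SD and high within-patient correlation.

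On design, the patient returns to 30° or supine between steps, lung fluid and tilt are recorded continuously, and at least an hour of stability is required before testing. It would be wrong to say that no resting readings exist before the 15° and right-side steps. They are collected; the protocol simply does not make them those steps' baselines. The 3 hours cover all four tests, so the drift within one test is shorter. The Section 4 expectation concerns upper-body position, so the left-right order bears on the body-position endpoint rather than on that sentence.

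What survives is that the order is fixed by the protocol itself, and no later analysis can undo it.

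**Conclusion.** The point holds in a limited form. The protocol states an expectation of no effect, gives no size of shift that would count as none, and relies on a sample justified for feasibility. Under any of the variants above, a non-significant posture change in 15 patients would be weak evidence of no effect, since the interval reaches roughly half an SD of the change either side. The exact miss rate (56% or 42% at 0.5 SD) depends on assumed alpha, sidedness and SD scale. No SD in ReDS units is available to say whether 0.5 SD matters.

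The firmer part is the design: 45° always before 15°, left always before right, and windows defined per test. Each position's effect is confounded with order and carry-over. The size of that bias cannot be given from the protocol. It warrants a change before enrolment but does not threaten the primary endpoint or the feasibility aim.

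**What to change.** In Section 5, alternate by patient which elevation step and which side comes first, where the patient's condition allows, and record the order used. Name the continuously recorded resting readings immediately before and after each step as that step's baseline.

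In Sections 4 and 5, say that the mean change will be reported with its confidence interval in ReDS volume-% units. Say also that no effect of position will be concluded only if the 90% interval lies within a margin fixed before data are seen. Otherwise the result is to be called descriptive, or not shown.

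A within-patient comparison of the leg-raise and upper-body changes may be added as supplementary. It does not test for no posture effect, because a sizeable posture effect would pass if the leg-raise effect were larger.

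The cost is slightly more complex bedside logistics, a margin to agree, and a posture result that may well be inconclusive with 15 patients (equivalence power about 20% for a 0.5 SD margin and 81% for 0.8 SD).
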